## 5.10 Treatment of Study Drug beyond Disease Progression

Patients will receive study drug until confirmed radiologic disease progression as assessed by investigator using RECIST v1.1 criteria, unacceptable toxicity or inability to tolerate further treatment, loss to follow-up, death, or withdrawal of consent.

If a patient receiving study drug has met criteria for confirmed radiologic disease progression by RECIST v1.1 criteria, but the patient continues to derive clinical benefit per the investigator, then continuation of treatment will be permitted. In such cases, the investigator's decision to continue treatment should be documented in the source documents and the sponsor's medical officer or designee should be informed. The patient must provide additional consent at their next scheduled study visit to continue treatment with study drug. Clinical scenarios where continuation of study drug after radiographic progression may be considered include 1) a patient for whom radiographic progression develops slowly while disease-related symptoms remain well controlled, 2) a patient who experiences progression in a site of disease that is unlikely to adversely affect prognosis (eg, enlargement of a solitary lymph node), or 3) a patient with general disease control but limited progression in sites of disease that can be managed with local therapies such as surgery or radiation. Patients continuing to receive study drug will continue to have all protocol-required assessments as described in [Section 7](#).

Continuation of treatment will be considered for a maximum cumulative duration of 24 months after initiation of oral/IV combination study treatment, or until confirmation of further progression as assessed by the investigator, whichever is sooner.

## 6 PRIOR AND CONCOMITANT THERAPY

Drug-drug interactions between nivolumab and rucaparib are unlikely (see [Section 1.1.3.2](#)).

### Cohorts A1 and A2 Ovarian:

Patients who have received prior treatment with a PARP inhibitor (PARPi), including IV or oral rucaparib or an immune checkpoint inhibitor for any previous malignancy are not eligible to participate in this study. Exception: patients who received a prior PARPi as front-line maintenance therapy and did not have disease progression on the PARPi, are eligible to participate in the study, providing inclusion criterion 11 is met at the time of screening.

All procedures performed (eg, thoracentesis, etc.) during the study must be documented on the eCRF.

### 6.1 Supportive Care

During the study, supportive care (eg, antiemetics; analgesics for pain control) may be used at the investigator's discretion and in accordance with institutional procedures. Supportive care must be recorded for each patient in the appropriate section of the eCRF.

Erythropoietin, darbepoetin alfa, and/or hematopoietic colony-stimulating factors for treatment of cytopenias should be administered per standard of care and according to institutional guidelines. Transfusion thresholds for blood product support will be in accordance with institutional guidelines.

### 6.2 Radiotherapy

Palliative radiotherapy on lesions not considered target lesions for tumor evaluation is permitted during the study. Treatment with study drug should be held prior to initiation of radiation therapy and until the patient has recovered from any radiation related toxicity.

### 6.3 Anticancer or Experimental Therapy

No other anticancer therapies (including chemotherapy, radiation, antibody or other immunotherapy, gene therapy, vaccine therapy, angiogenesis inhibitors, or other experimental drugs) of any kind will be permitted while the patient is participating in the study with the exception of palliative radiotherapy and hormonal treatment. Prior treatment with such excluded anticancer therapies must have been completed > 14 days prior to the first dose of study drug.

Any botanical preparations (eg, herbal supplements or traditional Chinese medicines) intended to treat the disease under study, or provide supportive care are prohibited (except those prescribed as supportive care by a health care professional as per [Section 6.1](#)).

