(Cohort A2) Have gBRCAmut ovarian cancer (ie, deleterious germline BRCA1/2 mutation, as determined by a local laboratory that has received an international or country specific quality standards certification).
  10. Be willing to have a mandatory biopsy of tumor tissue collected at Cycle 1 Day 28 of treatment.
  11. Have relapsed/progressive disease as confirmed by radiologic assessment
  12. Received 1 or 2 prior regimens, including  $\geq 1$  prior platinum based therapy and have platinum-sensitive disease:
    - a. Received  $\geq 1$  prior platinum-based treatment regimen; AND
    - b. Received a platinum-based regimen as their last treatment; continuous or switch maintenance treatment as part of this regimen is permitted (hormonal treatment may be permitted following the last platinum); AND
    - c. Was sensitive to the last platinum regimen. Platinum-sensitive disease is defined as documented radiologic progression  $> 6$  months after the last dose of platinum administered in the treatment setting.
  13. Have an ECOG performance status of 0 to 1  $\leq 14$  days prior to first dose of rucaparib.

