### 9.6.1 Primary Efficacy Analyses

The primary efficacy endpoint of ORR is defined as a best confirmed response of CR or PR by RECIST v1.1 as assessed by the investigator. The confirmed response rate by RECIST v1.1 is defined as the proportion of patients with a confirmed CR or PR on subsequent tumor assessment at least 28 days after first response documentation. The ORR will be summarized with frequencies and proportion together with 95% CI of the proportion using Clopper-Pearson methodology.

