### 9.6.2 Secondary Efficacy Analysis

#### 9.6.2.1 ORR Assessed by RECIST and GCIG CA-125 Criteria

The endpoint of ORR assessed by RECIST v1.1 or GCIG CA-125 criteria is defined as a best confirmed response of CR or PR using RECIST v 1.1 as assessed by the investigator or a confirmed response per GCIG CA-125 criteria. The endpoint of CA-125 response rate defined as at least a 50% reduction in CA-125 as assessed by GCIG criteria ([Appendix 2](#)). The response rate will be summarized with frequencies and percentages in addition to 95% CI of the proportion using Clopper-Pearson methodology. The combined ORR will be assessed as indicated in [Table 11](#).

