#### 9.6.2.3 Progression-free Survival (PFS)

Progression-free survival as assessed by investigator by RECIST is defined as the time from first dose to disease progression, according to RECIST v1.1 criteria as assessed by investigator, or death due to any cause, whichever occurs first. PFS will be calculated as 1+ the number of days from the first dose of study treatment to first occurrence of disease progression (per RECIST v1.1) or death due to any cause, whichever occurs first. For patients who continue treatment post-progression, the first date of progression (per RECIST v1.1) will be used for the analysis. Patients without a documented event of progression will be censored on the date of their last adequate tumor assessment (ie, radiologic assessment) or date of first dose of study treatment if no post-baseline tumor assessments have been performed. Only tumor scans prior to start of any subsequent anticancer treatment are included.

The Kaplan-Meier methodology will be used to summarize PFS. If able to be estimated, the 50th percentile (median) together with a 95% CI, will be presented based on log-log transformation. The number of patients with events and the number of censored patients will also be presented.

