### Evaluation of Best Overall Response

The best overall response is the best response recorded from the start of the treatment until disease progression/recurrence (taking as reference for PD the smallest measurements recorded since the treatment started).

Evaluation of Best Overall Response: Patients with Target (±Non-Target) Disease			
Target Lesions	Nontarget Lesions	New Lesions	Overall Response
CR	CR	No	CR
CR	Non-CR/non-PD	No	PR
CR	Not evaluated	No	PR
PR	Non-PD or not evaluated	No	PR
SD	Non-PD or not evaluated	No	SD
Not Evaluated	Non-PD	No	NE
PD	Any	Yes or No	PD
Any	PD	Yes or No	PD
Any	Any	Yes	PD

Evaluation of Best Overall Response: Patients with Non-Target Disease Only		
Nontarget Lesions	New Lesions	Overall Response
CR	No	CR
Non-CR/non-PD	No	Non-CR/non-PD a
Not all evaluated	No	NE
Unequivocal PD	Yes or No	PD
Any	Yes	PD

a 'Non-CR/non-PD' is preferred over 'stable disease' for non-target disease since SD is increasingly used as endpoint for assessment of efficacy in some studies so to assign this category when no lesions can be measured is not advised.

Patients with global deterioration of health status requiring discontinuation of treatment without objective evidence of disease progression at that time should be classified as having symptomatic deterioration. Every effort should be made to document the objective progression, even after discontinuation of treatment.

In some circumstances, it may be difficult to distinguish residual disease from normal tissue. When evaluation of CR depends on this determination, it is recommended that the residual lesion be investigated (fine needle aspiration/biopsy) prior to confirming the complete response status.

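### Hormonal anticancer treatment may be started during study treatment, but ORR and CA-125 response have no cut at its start, and the PFS and DOR rule does not say whether it counts

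*Combined protocol and SAP*

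**What the plan says.** **What is permitted.** Section 6.3 prohibits other anticancer therapies during participation, "with the exception of palliative radiotherapy and hormonal treatment". Section 6.2 limits the radiotherapy: "Palliative radiotherapy on lesions not considered target lesions for tumor evaluation is permitted during the study". Inclusion criterion 12b (Section 4.2) notes that "hormonal treatment may be permitted following the last platinum". Hormonal treatment is not named in the 14-day washout list of exclusion criterion 14 (Section 4.3).

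**Response endpoints.** Section 9.6.1 states: "The primary efficacy endpoint of ORR is defined as a best confirmed response of CR or PR", by RECIST v1.1 per investigator. Appendix 1 sets the window: "The best overall response is the best response recorded from the start of the treatment until disease progression/recurrence". Section 9.6.2.1 says: "The endpoint of CA-125 response rate defined as at least a 50% reduction in CA-125 as assessed by GCIG criteria", and Table 11 combines this with RECIST. Appendix 2 makes a patient non-evaluable for CA-125 after mouse antibodies or recent interference with the peritoneum or pleura. It does not mention hormonal treatment.

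**Time-to-event endpoints.** Sections 9.6.2.3 (PFS) and 9.6.2.4 (DOR) carry the same sentence: "Only tumor scans prior to start of any subsequent anticancer treatment are included".

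**The concern.** The exemption in Section 6.3 is an exemption from a ban on anticancer therapy, so it covers hormonal agents given for the tumour and not only hormone replacement. Such an agent is systemic and could act on target lesions and on CA-125. The response definitions run to progression with no other stopping point, so a response that appears after the agent is added counts for the combination. Cohort A1 has no control arm, so nothing in the design separates the two contributions, and the primary result is judged against a fixed 10%.

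For PFS and DOR the problem is different. A cut exists, but an analyst cannot tell from the text whether a permitted concurrent agent triggers it. Two analysts could derive different times from the same data.

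**Working it through.** **Step 1. Which endpoints react to an on-study hormonal agent?**

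| Endpoint | Where defined | Cut at start of a hormonal agent? |
|---|---|---|
| ORR | 9.6.1, Appendix 1 | None |
| CA-125 and combined response | 9.6.2.1, Table 11, Appendix 2 | None |
| PFS | 9.6.2.3 | Only if it is *subsequent* treatment; undefined |
| DOR | 9.6.2.4 | Same as PFS |

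Section 7.5.2 collects subsequent anticancer treatments after discontinuation of study treatment. On that usage a concurrent agent would not trigger the PFS and DOR cut, but this is an inference from usage and not a stated rule.

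**Step 2. Who is exposed?** Criteria 11 and 12c require radiologic progression before entry. A patient whose hormonal agent began before that progression has already progressed on or after it. The relevant patients are those who start an agent between progression and first dose, or who start or change one on study.

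**Step 3. Reproduce the design.** Inputs from Section 9.2.1: optimal Simon design, null 10%, alternative 25%, 5% and 80%, 18 then 43 patients, continue if at least 3 of 18 respond. The final cut-off is not printed. With X1 the responders among the first 18 and X2 those among the next 25:

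P(pass | p) = Σ (x = 3 to 18) P(X1 = x) · P(X2 ≥ 8 − x)

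- p = 0.10: 0.0480
- p = 0.25: 0.8003

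A search for the smallest expected sample size under the null returns 2/18 and 7/43, so the implied pass mark is at least 8 of 43. The stated design is reproduced, and no sample-size figure is in error. These figures treat stage 1 as a binding stop.

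**Step 4. One extra credited responder.** One patient is 1/43 = 2.3 percentage points of ORR. If one response is credited at the final analysis only, the pass mark on true responses falls to 7 of 43:

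Σ (x = 3 to 18) P(X1 = x) · P(X2 ≥ 7 − x) at p = 0.10 gives 0.0940.

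**Step 5. Range under assumed use.** The documents give neither frequency of use nor response rate, so both are assumptions. Let f be the share of patients using such an agent and q the share of otherwise non-responding users credited with a response. The effective null rate is 0.10 + 0.90·f·q.

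| f | q | Effective null rate | P(pass) |
|---|---|---|---|
| 5% | 5% | 0.1023 | 0.0535 |
| 10% | 10% | 0.109 | 0.0721 |
| 10% | 20% | 0.118 | 0.1027 |
| 20% | 20% | 0.136 | 0.1822 |

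**The case against.** **PFS and DOR are not without a rule.** A reader might infer that nothing in the efficacy sections responds to another therapy. That is not so: both endpoints exclude scans after subsequent anticancer treatment. What stands is that the term is undefined.

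**Radiotherapy.** A reader might extend the point to palliative radiotherapy as a source of ORR. The documents do not support that. It is limited to non-target lesions, while a partial response is defined in Appendix 1 by the target-lesion sum. Turning a PR into a CR does not change ORR. The remaining route is averted non-target progression, and Appendix 1 calls overall progression on non-target disease alone, with target disease stable or responding, extremely rare. The local-therapy scenario in Section 5.10 arises after progression, when PFS, DOR and best response are already closed. A small effect on PFS or DOR remains possible.

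**Size.** A reader might take 2.3 points as a shift in the true null rate, from 10% to 12.3%, which gives a pass probability of 0.122. One extra responder gives 0.094. The larger figure requires 0.90·f·q = 0.023: at q = 10%, f = 0.256, or about 11 of 43 patients; at q = 20%, 5 to 6 patients. Nothing in the documents indicates such use, and with 5% for both inputs the probability barely moves.

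**Data and deferral.** Concomitant medications are recorded through the 100-day visit (Section 7.5.2), so users can be identified. Section 9.1 defers further detail to a SAP, and the available text contains no separate SAP, so a rule may exist elsewhere. Both points make the fix easier; neither supplies the rule.

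**Conclusion.** The point holds for hormonal treatment. ORR and CA-125 response have no cut when a permitted hormonal agent starts, and the PFS and DOR cut rests on an undefined term. A response could be credited to the combination; the documents do not show that any will be.

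The bias cannot be sized from the documents. One credited responder at the final analysis would roughly double the false-positive probability, from 0.048 to 0.094. Under the assumed use in the table it ranges from 0.0535 to 0.1822. All of these rest on the derived 8-of-43 pass mark and a binding stage 1 stop. For palliative radiotherapy the documents support no claim about ORR and only a limited question for PFS and DOR.

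**What to change.** Leave the concomitant-treatment rule as it is and change the analysis text, before response data are reviewed:

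- **ORR and CA-125 or combined response:** count only assessments before the start or change of a hormonal agent given for the cancer.
- **PFS and DOR:** define subsequent anticancer treatment and state whether such an agent counts.
- **Data:** record indication on the concomitant medication eCRF, so that agents given for the tumour can be told apart from others.
- **Sensitivity ORR:** exclude responses in patients who started a hormonal agent between progression and first dose.
- **Palliative radiotherapy to non-target lesions:** list the patients and run a PFS/DOR sensitivity analysis. Do not make it a primary censoring event. Patients who need it may be close to progression, so censoring could be informative and could raise the Kaplan-Meier estimate.

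The cost is SAP wording, one eCRF field, a listing and the sensitivity analyses. ORR may be slightly lower, partly because a response awaiting its confirmatory scan (at least 28 days later) when the agent starts would not count.

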### 6.4 CYP450 Isoenzyme Inhibitors, Inducers, and Substrates

Based on the results from the in vivo CYP interaction study (Study CO-338-044), rucaparib is a moderate inhibitor of CYP1A2, and a weak inhibitor of CYP2C9, CYP2C19, and CYP3A.

Caution should be used in patients on rucaparib taking concomitant medicines that are substrates of CYP1A2, CYP2C9, CYP2C19, and/or CYP3A with narrow therapeutic windows ([Appendix 4](#)). Selection of an alternative concomitant medication is recommended.

Although in vitro rucaparib metabolism mediated by CYP3A4 was slow, a significant contribution of CYP3A4 in vivo cannot be excluded. Caution should be used for concomitant use of strong CYP3A4 inhibitors or inducers ([Appendix 5](#)).

## 6.5 Anticoagulants

Rucaparib is a weak inhibitor of CYP2C9 in vivo. Caution should be exercised in patients receiving rucaparib and concomitant warfarin (Coumadin). Patients taking warfarin should have international normalized ratio (INR) monitored regularly per standard clinical practice.

## 6.6 Immunosuppressive Agents

Immunosuppressive agents are prohibited, with the exception of inhaled or topical steroids, and adrenal replacement steroid doses > 10 mg daily prednisone equivalent, in the absence of active autoimmune disease. Patients are permitted the use of topical, ocular, intra-articular, intranasal, and inhalational corticosteroids (with minimal systemic absorption). Adrenal replacement steroid doses > 10 mg daily prednisone are permitted. A brief (less than 3 weeks) course of corticosteroids for prophylaxis (eg, contrast dye allergy) or for treatment of non-autoimmune conditions (eg, delayed-type hypersensitivity reaction caused by a contact allergen) is permitted.

Patients with a condition requiring systemic treatment with either corticosteroids (> 10 mg daily prednisone equivalent) or other immunosuppressive medications within 14 days of treatment assignment are excluded.

## 6.7 Other Concomitant Medications

Therapies considered necessary for the patient's well-being may be given at the discretion of the investigator and should be documented on the eCRF. Other concomitant medications, except for analgesics, chronic treatments for concomitant medical conditions, or agents required for life-threatening medical problems, should be avoided. Any botanical preparations (eg, herbal supplements or traditional Chinese medicines) intended to treat the disease under study, or provide supportive care are prohibited (except those prescribed as supportive care by a health care professional). Any botanical preparations taken by the patient should be documented appropriately on the eCRF.

Rucaparib marginally increased digoxin AUC by 20%. Caution should be exercised for patients receiving rucaparib and requiring concomitant medication with digoxin. Patients taking digoxin should have their digoxin levels monitored after starting rucaparib and then regularly per standard clinical practice.

In vitro, rucaparib is a potent inhibitor of MATE-1 and MATE2-K, a moderate inhibitor of OCT1, and a weak inhibitor of OCT2. As inhibition of these transporters could decrease metformin renal elimination and decrease liver uptake of metformin, caution is advised when metformin is co-administered with rucaparib. In addition, rucaparib is an inhibitor of the BCRP

with IC50 value suggesting potential BCRP inhibition and increased exposures of medicinal products that are BCRP substrate (eg, rosuvastatin).

Although in vitro rucaparib metabolism mediated by CYP3A4 was slow, a significant contribution of CYP3A4 in vivo cannot be excluded. Caution should be used for concomitant use of strong CYP3A4 inhibitors or inducers.

## **6.8 Imaging Restrictions and Precautions**

It is the local imaging facility's responsibility to determine, based on patient attributes (eg, allergy history, diabetic history, and renal status), the appropriate imaging modality and contrast regimen for each patient. Oral and/or IV contrast should be used whenever possible and appropriate, and rectal contrast should only be considered in patients with peritoneal disease. Imaging contraindications and contrast risks should be considered in this assessment. Patients with renal insufficiency should be assessed as to whether or not they should receive contrast and if so, what type and dose of contrast is appropriate. Specific to MRI, patients with severe renal insufficiency (ie, estimated GFR < 30 mL/min/1.73 m^2) are at increased risk of nephrogenic systemic fibrosis. MRI contrast should not be given to this patient population. In addition, patients are excluded from MRI if they have tattoos, metallic implants, pacemakers, etc.

The ultimate decision to perform MRI in an individual patient in this study rests with the site radiologist, the investigator and the standard set by the local IEC.

## **6.9 General Restrictions**

Photosensitivity has been observed in patients treated with rucaparib. Patients should avoid spending time in direct sunlight because they burn more easily during treatment with rucaparib. When outdoors, patients should use typical precautions such as applying sunscreen (sun protection factor 50 or greater) and/or covering exposed skin with clothing and wearing a hat and sunglasses.

## 7 STUDY PROCEDURES AND METHODS

### 7.1 Schedule of Assessments

[Table 6](#) summarizes the procedures and assessments to be performed for all patients. Study procedures and assessments should be performed as close to the scheduled time as possible, but within  $\pm 3$  days of the scheduled time unless otherwise stated.

[Table 7](#) summarize the timing of collection of PK and immunogenicity samples.

[Table 8](#) and [Table 9](#) summarize the timing of peripheral blood biomarker sample collection.

Applicable imaging guidelines should be followed for the collection of images and the radiological assessment of disease.

Tumor tissues (screening and optional sample at the time of disease progression), PK samples, and ctDNA, biomarker samples will need to be sent to central laboratories for processing. Clinical chemistry, hematology, urinalysis, pregnancy testing, serology testing, CA-125, and ECG will be conducted at a local laboratory. Please refer to study laboratory manuals for detailed collection, processing, and shipment requirement.

